- q. Mutation analysis of the BCR-ABL1 transcript will be performed using a peripheral blood sample collected at the end-of-treatment visit in order to identify mutations acquired upon treatment with bosutinib. Mutations will be identified by direct sequencing of the BCR-ABL transcript performed at a Central Laboratory as arranged by the Sponsor. Peripheral blood from all eligible patients (except from patients enrolled at sites in China) will be collected and shipped frozen to a central vendor for analysis. Specific instructions for handling and shipment of these samples can be found in Study Reference Manual.

B. Schedule of Activities for CML 2nd line or patients coming from Study B1871006

Study Visit	Initial ^a	On Treatment			End of Treatment	Long-Term Follow-Up LTFU
		Site visit At Month 3 ^l	Every 6 months ^b	Phone call Every 3 months ^c		
Schedule	≤28 days from last dose on parent study				≤28 days after last dose of bosutinib	Every 3 months ^b
ICD signature	X					
Eligibility criteria review	X					
Bosutinib Administration	Continuous Daily Dosing					
Physical Examination	X ^d				X	
Vital Signs	X ^d				X	
ECOG	X ^d				X	
Extramedullary Assessment	X ^d		X		X	
Chest X-Ray	X ^d	As clinically indicated			X	
ECHO or MUGA	X ^d	As clinically indicated			X	
ECG	X ^d	As clinically indicated			X	
Hematology ^c	X ^d		X		X	
Biochemistry ^f	X ^d		X		X	
Liver function tests ^g	X ^d		X		X	
Coagulation Panel ^h	X ^d				X	
Serum pregnancy test	X ^d	As clinically indicated			X	
Dipstick Urinalysis ⁱ	X ^d				X	
Bone Marrow Aspirate or Peripheral Blood for Cytogenetics (Karyotyping or FISH) or Molecular Analysis per local practice standards ^j	X ^k		X		X	
AEs and concomitant medications ^k	X	X	X	X	X	
Collection of diarrhea information ^l	X	X				
Survival follow-up						X ^m
PK sample collection ⁿ		Refer to footnote n	Refer to footnote n		Refer to footnote n	
Contraception Check ^o	X	X	X	X	X	
IP dispensation, dosing check ^p		X	X	X	X	
Bcr-Abl Mutation analysis ^q					X	

- For patients who have already discontinued bosutinib in the parent study and directly enter in the long-term follow-up phase of this extension study, the procedures will include ICD signature; collection of data on any subsequent TKI therapy or other anti-cancer treatment and response to other treatment (if applicable) following discontinuation of bosutinib, and survival data.
- 1 month is defined as a 4-week or 28-day period. Study visit can be performed with a ±2 week (14-day) window.

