6.2. Study Period

Visit schedules and study procedures will be different based on the line of treatment of the patients (ie, if enrolled from B1871006 vs. B1871008). Study visit can be performed with a ± 14 -day (2-week) window (1 month is defined as a 4-week or 28-day period).

- 1st line chronic phase patients enrolled from study B1871008 will be followed up only to collect safety, survival and BCR-ABL mutational status data (the latter does not apply to patients enrolled at China Sites). Study visits will occur every 12 months (once a year), and a phone call will be implemented every 3 months between study visits at the site in order to collect an update on the patient's current safety status and dosing and to remind the patient about use of the dosing diary and importance of contraception compliance. All information collected during the phone calls will be immediately recorded in the eCRF.

One additional study visit will be arranged after the first 3 months ± 4 days of treatment in order to collect all diarrhea information reported on the patient diarrhea card provided at the baseline visit.

Patients who are continuing bosutinib therapy should have their disease status assessed according to the local standard of care.

- For 2nd and later line patients enrolled from study B1871006, study visits will occur every 6 months (twice a year) and a phone call will be implemented every 3 months, between scheduled visits in order to get an update on current patient's status, assessment of any adverse events, and dosing compliance, and a contraceptive check.

Procedures performed as part of the study visits may include:

- Extramedullary disease assessment;
- According to standard of care and current treatment guidelines, bone marrow or blood sample will be collected for CML disease assessment via cytogenetic assessment by karyotype or by FISH. If appropriate, in lieu of cytogenetic assessment molecular response monitoring using reverse transcriptase polymerase

chain reaction (RT-PCR) for molecular assessment (of BCR-ABL fusion transcript levels in peripheral blood may be performed. These assessments will be performed at a laboratory local to Investigational Site and data will be collected if available.

- Hematology panel with complete blood counts (CBC) (see [Section 6.1](#) for details);
- Chemistry panel (see [Section 6.1](#) for details);
- Liver Function Tests (LFTs) (see [Section 6.1](#) for details);

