6.1. Efficacy Endpoint(s)

- Duration of major/complete cytogenetic response (MCyR/CCyR) for B1871006 patients only;
- Duration of major/deep molecular response (MMR/MR4) for B1871006 patients only;
- Duration of complete hematologic response (CHR) for B1871006 patients only;
- Duration of overall hematologic response (OHR) for B1871006 advanced patients only;
- Progression-free survival (PFS) for B1871006 patients only;
- Transformation to accelerated or blast phase for B1871006 patients only;
- BCR-ABL mutations present at treatment discontinuation;
- Overall Survival (OS).

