Molecular response in B1871006 was based on the difference between the subject's change in Bcr-Abl/Abl ratio and a laboratory reference baseline. The Quest (vendor) laboratory reference Bcr-Abl/Abl ratio of 4.1325 derived from a pool of 120 previously untreated CML subjects was used as the standardized (or reference) baseline. Molecular response was not analyzed for subjects in China, India, the Russian Federation, and South Africa due to logistical constraints in transporting samples to the central laboratory.

To be considered a responder for MMR in B1871006, a subject must have had at least a 3-log reduction from the Quest standardized baseline, a detectable Bcr-Abl transcript at baseline or any time post-baseline, and must have maintained or attained a CCyR. Additionally, as a conservative approach given the known variability with standard MMR analyses, a subject who had a non-CCyR on the same day as the MMR assessment was not considered to have a MMR at that time point. MR⁴ was defined similar to MMR except at least a 4-log reduction was required. In B1871040, responders had MMR/MR⁴ or better denoted on the CRF as assessed by a local laboratory. On-treatment response is independent of a patient's baseline molecular response.

PFS is defined as the time from first dose to progression as assessed by the investigator and noted as the reason for permanent treatment discontinuation on the CRF or on-treatment death due to any cause ($[\text{date of progression/death} - \text{first dose date}]/30.4$), whichever occurs first. Patients without events are censored at the last cytogenetic, hematologic, or laboratory assessment where progression could be assessed. Progression for B1871006 patients is defined as:

- *Evolution from chronic phase (or from return to chronic phase for advanced subjects) to accelerated phase or blast crisis (on two consecutive assessments at least a week apart).*
- *Evolution from accelerated phase to blast crisis (on two consecutive assessments at least a week apart).*
- *One of the following conditions occurring after dose escalation or presence of adverse events prohibiting dose escalation:*
 - *For 2nd or later line subjects, loss of major cytogenetic response (need at least 30% increase).*
 - *For all lines of treatment, loss of complete hematologic response confirmed by 2 assessments at least 2 weeks apart.*

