 - *For all lines of treatment, increasing WBC defined as doubling of WBC, occurring over a period of ≥ 1 month, with the second WBC $> 20 \times 10^9/L$ and confirmed at least 1 week later.*

For DOR and PFS, if there is an unacceptable gap between the date of progression or death and the date of the most recent prior disease assessment (>48 weeks), the event will not be used and censorship will be at the most recent prior assessment.

Transformation, defined by the first two progression bullets above, is the time from first dose to confirmed transformation ($[\text{date of transformation} - \text{first dose date} + 1]/7$). Confirmed transformation is defined as 2 consecutive assessments at least 1 week apart or 1 assessment confirmed by progression of disease or death. Patients without events are censored at the last hematologic or extramedullary assessment where transformation could be assessed.

BCR-ABL mutational status at treatment discontinuation will be assessed. Emergent mutations are defined as those mutations which were not present at baseline. B1871006 patients who were not assessed for baseline mutations are not assessable for emergent mutations. All B1871008 patients are assessable for emergent mutations.

OS is defined as the time from randomization for B1871008 patients and from first dose B1871006 patients to the date of death ($[\text{date of death} - \text{randomization/first dose date}]/30.4$). Patients who have not died will be censored at the last known alive date.

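### The 48-week gap rule for DOR and PFS equals two 24-week visit intervals with no window allowance, so after one missed extension visit a few days of permitted timing can decide whether an event counts

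*SAP*

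**What the plan says.** - **The rule.** SAP 6.1 applies it to DOR and PFS. The gap runs from the progression or death back to "the date of the most recent prior disease assessment (>48 weeks), the event will not be used", and the patient is censored at that earlier assessment. The SAP gives no reason for 48 weeks, does not mention the visit window, and does not define a disease assessment for this purpose.
- **Who is affected.** SAP 6.1 lists "Progression-free survival (PFS) for B1871006 patients only", and restricts the DOR endpoints in the same way. The yearly visits of B1871008 patients therefore play no part.
- **Visit spacing.** For these patients Protocol 6.2 states that "study visits will occur every 6 months (twice a year"). A footnote to Protocol Table 1 B says "1 month is defined as a 4-week or 28-day period. Study visit can be performed with a ±2 week (14-day) window", and Protocol 6.2 repeats both the month definition and the window.
- **The PFS event.** It is "progression as assessed by the investigator and noted as the reason for permanent treatment discontinuation on the CRF", or on-treatment death. Otherwise, "Patients without events are censored at the last cytogenetic, hematologic, or laboratory assessment where progression could be assessed".
- **Where the rule is absent.** SAP 6.1 sets no gap rule for time to transformation or OS. Protocol 9.5 and 9.6 define PFS and DOR without one.

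**The concern.** A gap rule is meant to exclude events found so long after the last look that their date is uninformative. To do that consistently it has to separate one missed visit, which is ordinary, from a longer lapse. A limit equal to exactly two intervals cannot do this when each visit may move by two weeks. Two patients with the same history, each missing one visit and each attending the next within the permitted window, can be treated in opposite ways: one has an event, the other is censored months earlier.

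The direction of the error is known. A removed event becomes a censored time that precedes it, which raises the Kaplan-Meier estimates of DOR and PFS. Duration of clinical benefit is a stated objective (Protocol 2.1).

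**Working it through.** **Inputs.** Limit: >48 weeks = >336 days (SAP 6.1). Month: 28 days; window: ±14 days (Protocol Table 1 B footnote and 6.2). Interval: 6 months, which is 6 × 28 = 168 days (24 weeks) or, at two visits a year, 182 days (26 weeks; 182.625 days by the calendar). Assumption, not in the documents: each visit falls on any whole day from −14 to +14 with equal probability, independently.

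**The plan's figure.** 2 × 6 × 28 = 336 days = 48.0 weeks. The limit matches two 28-day-month intervals exactly.

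**Range of gaps.** With k missed visits, gap = (k + 1) × interval + (e2 − e1), where e1 and e2 each lie in −14 to +14, so the spread is ±28 days.

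| Missed visits | 24-week spacing | 26-week spacing |
|---|---|---|
| 0 | 20–28 weeks | 22–30 weeks |
| 1 | 44–52 weeks | 48–56 weeks |
| 2 | 68–76 weeks | 74–82 weeks |

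The 48-week limit falls in the middle of the one-missed-visit range at 24 weeks and at its lower end at 26 weeks. At either spacing, any limit from the top of that range up to 68 weeks (24-week) or 74 weeks (26-week) would separate one missed visit from two.

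**Share discarded: one missed visit, event dated at the next scheduled visit, nothing assessed in between.** There are 29 × 29 = 841 pairs of visit days.
- 24 weeks: discarded if e2 > e1. Ties are kept: 29/841 = 3.4%. Discarded: (841 − 29)/2 = 406, and 406/841 = 48.3% (50% in continuous time).
- 26 weeks: kept only if e2 − e1 = −28, one pair in 841. Discarded: 840/841 = 99.9%. At 182.625 days it is 100%.

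**Sensitivity to window use, 24 weeks, prior visit on its nominal day.** Later visit on time or late (0 to +14): 14/15 = 93%. On time or early (−14 to 0): 0%.

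**Events dated between visits.** This applies to deaths and to progressions found outside the schedule. Let the date be uniform between the missed visit and the next due visit.
- 24 weeks: only an early prior visit can push the gap past 336 days. Mean share = (1 + 2 + … + 14)/(29 × 168) = 105/4,872 = 2.2%.
- 26 weeks: (364 − 336)/182 = 15.4%. At 182.625 days: (365.25 − 336)/182.625 = 16.0%.

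**Effect of a window-adjusted limit.**
- 24 weeks: 336 + 28 = 364 days = 52 weeks.
- 26 weeks: 364 + 28 = 392 days = 56 weeks.
- Discards after one missed visit fall to 0% in each case (0.4% at 182.625 days with a 56-week limit).
- A 52-week limit with 26-week spacing would still discard 48.3%.
- Both limits still exclude events after two missed visits.

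**The case against.** The strongest reply is that the plan does not confine detection of progression to scheduled visits. PFS progression is the investigator's judgement at discontinuation. Unplanned visits are allowed (introduction to Protocol Table 1), and phone contact falls between visits. Disease testing follows local practice, and hematology is repeated within 4 weeks if CHR is lost. Any such assessment shortens the gap. If progression is dated at the confirming assessment, the first abnormal one may count as the prior assessment and the rule would not fire. This stands, and it is why the 48–50% and near-100% figures are conditional.

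The 26-week case rests on a parenthesis, while the 28-day month is an explicit definition. At exactly 24-week spacing, an event on the nominal day after one missed visit has a gap of 48 weeks and is kept. That is true, but attendance a day late reverses it, and the two descriptions of the interval still need reconciling.

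On-treatment patients receive a supply or prescription at least every 6 months (Protocol 5.4.1), so skipping a visit while staying on drug may be uncommon. That is plausible, but the documents give no rate.

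There is no hypothesis or decision rule (SAP 4), OS and transformation are untouched, and reasons for discontinuation are summarized separately (SAP 8.2.2.2). This limits the consequence. It does not explain why the limit sits inside the one-missed-visit range.

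**Conclusion.** The point holds as a conditional one. In the extension period, 48 weeks falls within, or at the bottom of, the range of gaps that one missed visit produces. Permitted visit timing can then decide whether a real event counts. For events dated at the next scheduled visit with no interim assessment, 48–50% are discarded at 24-week spacing and nearly all at 26, given uniform use of the window. At 24 weeks, one-sided use gives 0–93%. For events dated between visits the share is about 2% (24 weeks) to 16% (26 weeks).

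A reader might infer that any true progression after a missed visit is lost half the time, or always. The documents do not support that: they neither tie progression to scheduled visits nor say how the window is used.

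A reader might also want to turn these shares into percentage points of PFS. That cannot be done. No missed-visit rate is given. The curves also start at first dose in B1871006, whose visit schedule is not in the documents, so an extension-period discard rate cannot be applied to all events. The bias is upward for extension-period DOR and PFS, and its size is unknown.

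**What to change.** For B1871040 assessments:
1. Reconcile the 24-week and 26-week descriptions of the visit interval, and state which one the rule uses.
2. Set the limit at two intervals plus both windows: >52 weeks for 24-week spacing or >56 weeks for 26-week spacing. Alternatively, define it as two or more consecutive missed scheduled assessments.
3. State what counts as a disease assessment, and whether a confirmed progression is dated at the first or the confirming assessment.
4. Report the number of DOR and PFS events removed by the rule, and add a sensitivity analysis that counts them as events.

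This needs a few lines of SAP text and no new data. Its price is that a few events after one missed visit are kept with a less precise date. SAP 8.2.1 records that all but one extension patient had reached 10 years of follow-up before 11 March 2020, so a change now is late and should be labelled as such. If the limit is left alone for that reason, items 3 and 4 still show how much depends on it.

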6.2. Safety Endpoints

Treatment-emergent adverse events (TEAE) were defined as any event increasing in severity from baseline or any new event starting during bosutinib therapy or within 30 days of the last dose of study drug.

6.2.1. Exposure and Compliance

Exposure and compliance data will be collected during this study. The primary exposure endpoints while the patient is on treatment are duration of treatment, cumulative dose received, and reasons for dose modifications (reduction, delay, or escalation). Duration of treatment is the time from first non-zero dose to last non-zero dose ($[(\text{date of last non-zero dose} - \text{first dose date} + 1)/30.4]$). Planned dose is based on the initial dose for B1871006 patients and randomized dose for B1871008 patients.

6.2.2. Laboratory Evaluations, Vital Signs, and Cardiac Evaluations

Laboratory values, vital signs, electrocardiogram (ECG), and left ventricular ejection fraction (LVEF) data from echocardiogram (ECHO) or multiple gated acquisition scan (MUGA) will be collected during this study. Collection time points for these measurements are specified in the protocol. Laboratory values, vital signs, ECG, and LVEF data will be flagged according to the potentially clinically important (PCI) criteria for abnormal values. The PCI criteria for laboratory and LVEF values are those with grade 3 or 4 from NCI CTC version 3.0. The PCI criteria for vital signs and ECG are specified in [Appendix 3](#).

For continuous ECG parameters, the average of all valid measurements among the last performed “triplicate” ECG observed prior to taking the first dose of test article is defined as the baseline value. For Overall Evaluation, the most serious of all valid measurements among the last performed “triplicate” ECG observed prior to taking the first dose of test article is defined as the baseline value.

If multiple post-baseline observations occur at the same visit, the values used for summaries and analyses are defined as the following:

- For PCI laboratory evaluations, PCI vital signs (and body weight), and PCI LVEF, the most serious (highest grade) evaluation will be used for all summaries and analyses.
- For PCI ECG, the mean of the “triplicate” ECGs at each visit will be calculated and then the most serious (highest) mean will be used for all summaries and analyses. For Overall Evaluation, the most serious evaluation will be used for all summaries and analyses.

6.2.3. Laboratory Evaluations of Special Interest

Laboratory parameters including alanine aminotransferase (ALT), aspartate aminotransferase (AST), platelets, neutrophils, and hemoglobin will be summarized. Endpoints for these parameters include distribution of maximum toxicity, time to first event (time from first dose to date of first event including only non-partial dates), duration of any grade event (time from start date to stop date including only non-partial dates), and cumulative duration of grade

3/4 events (sum of time from start date to stop date including only non-partial dates for all events).

A listing will be provided for patients who potentially meet the Hy's law criteria. Potential is defined as meeting these 3 criteria any time during the study (non-concurrent): AST or ALT level of ≥ 3 x upper limit of normal (ULN), total bilirubin level of >2 x ULN, and alkaline phosphatase level <2 x ULN. Total Bilirubin, AST, ALT, and alkaline phosphatase will be listed.

6.2.4. Non-study Medications

Non-study medications are coded using the World Health Organization (WHO) Drug Dictionary. The Prior, Concomitant, After (PCA) flag for non-study medications will be derived: prior non-study medications are defined as any non-study medications taken before the first dose of test article administration; concomitant non-study medications are defined as any medications taken during the treatment period (includes the 30 days after the last dose of the test article); after non-study medications are defined as any non-study medications taken during the follow-up period.

6.2.5. Death

Death data will be collected during this study. Mandatory variables captured are date of death and cause of death. Deaths within 30 days of last dose and death due to AEs are safety endpoints.

6.2.6. Adverse Events

A 3-tier approach will not be used to summarize AEs since only the bosutinib patients from the randomized B1871008 are eligible for this study; the imatinib patients were not offered enrollment to this extension protocol. Furthermore, the B1871006 study was a single-arm non-comparative study.

To ensure accuracy and consistency in data analysis and reporting, all adverse events must be classified using the Medical Dictionary for Regulatory Activities (MedDRA) before database lock (DBL). The severity of AEs will be assessed using the National Cancer Institute Common Terminology Criteria for Adverse Events (NCI CTCAE) version 3.0. The causal relationship between test article and an AE will be assessed by investigator's judgment.

AEs will be classified as follows:

- TEAEs;
- AEs leading to treatment discontinuations;
- TEAEs leading to dose reductions;
- TEAEs leading to dose delays;
- TEAEs by maximum toxicity grade (grades 1 to 5);

- TEAEs of higher toxicity grades (grades 3 or 4);
- TEAEs related to test article;
- Serious adverse events (SAEs).

6.2.7. Adverse Events of Special Interest

Adverse events including ALT, AST, thrombocytopenia (including MedDRA preferred term [PT] Platelet Count Decreased), neutropenia (including PT Neutrophil Count Decreased), anemia (including PT Hemoglobin Decreased), diarrhea, nausea, vomiting, cardiac toxicity (definition to be determined before DBL), vascular toxicity (definition to be determined before DBL), and renal toxicity (definition to be determined before DBL) will be summarized. Additional AEs or AE clusters may be summarized if deemed appropriate. AE characteristics to be summarized include maximum toxicity, time to first event, duration of any grade event, cumulative duration of grade 3/4 events, and successful rechallenge (those patients who were re-dosed and did not discontinue bosutinib due to this AE after having a dose delay).

The diarrhea characteristics will also be summarized separately for data from B1871008 and B1871006 compared to B1871040 in order to assess the impact of changing to the clinical formulation of bosutinib from the parent studies to the commercial formation in this study. For ongoing events at the time of the switch to commercial formulation, the stop date for the event attributed to the clinical formulation will be set to date of the start of commercial formulation minus one and the start date for the event attributed to the commercial formulation will be set to the start date of commercial formulation.

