A total of 164 patients with advanced Ph⁺ leukemia were enrolled and treated in B1871006. The primary population for the efficacy response analyses was the evaluable population, which included all patients with an adequate baseline assessment for the respective endpoint. In AP CML patients in the evaluable population (n=69), the confirmed overall hematologic response (OHR) rate by Week 48 was 55.1%. In BP CML patients in the evaluable population (n=60), the confirmed OHR rate by Week 48 was 28.3%.

Summary safety data across all patient cohorts in B1871006 showed most patients (560, 98%) reported at least 1 drug-related treatment-emergent adverse event (TEAE). Treatment-related TEAEs reported in ≥10% of patients were diarrhea in 454 (80%) patients, nausea in 238 (42%) patients, vomiting in 195 (34%) patients, thrombocytopenia in 167 (29%) patients, rash in 157 (28%) patients, abdominal pain in 97 (17%) patients, alanine aminotransferase (ALT) increased in 91 (16%) patients, anemia, fatigue, and neutropenia in 81 (14%) patients each, abdominal pain upper in 76 (13%) patients, and aspartate aminotransferase (AST) increased in 71 (12%) patients.

Treatment-related TEAEs of Grade 3 or higher included thrombocytopenia in 117 (21%) patients, neutropenia in 58 (10%) patients, diarrhea in 44 (8%) patients, ALT increased in 36 (6%) patients, and rash in 32 (6%) patients.

As of February 15, 2012, 134 (23.5%) patients have permanently discontinued bosutinib treatment because of AEs. The most frequent AEs that led to discontinuation were thrombocytopenia (26 patients, 4.6%), ALT increased (11 patients, 1.9%), neutropenia (8 patients, 1.4%), diarrhea and vomiting (7 patients, 1.2% each).

First-Line CP CML

In the Phase 3 study 3160A4-3000-WW (B1871008), bosutinib was compared to imatinib in the frontline treatment of CP Ph⁺ CML. The primary objective of the study was to compare the complete cytogenetic response (CCyR) at one year in CP patients receiving bosutinib alone versus patients receiving imatinib alone. The study enrolled 502 pts (250 on bosutinib

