Compared with imatinib, bosutinib was associated with higher incidences of Grade 3-4 gastrointestinal toxicities, including diarrhea (12% vs. 1%), vomiting (3% vs. 0%) and abdominal pain (1% vs. <1%), although these adverse events were usually transient and manageable. Notably, diarrhea occurred mostly in the first 1-2 months of therapy and improved or subsided spontaneously over time. The rates of Grade 3-4 non-hematologic toxicities were $\leq 1\%$ in both arms of the study. Grade 3-4 elevations of alanine aminotransferase (23% vs. 4%), aspartate aminotransferase (12% vs. 4%) or lipase (11% vs. 6%) were more frequent among patients treated with bosutinib compared to imatinib. Of those patients experiencing Grade 3-4 elevations in transaminase levels in the bosutinib arm of this study, 91% were rechallenged. Of these patients, 80% did not experience subsequent elevations in transaminase levels that merited treatment discontinuation. Overall, 14% of patients were discontinued from bosutinib treatment due to unacceptable transaminase elevations. Grade 3-4 neutropenia, thrombocytopenia and anemia in the bosutinib and imatinib arms were 10% vs. 24%, 14% vs. 15% and 8% vs. 8%, respectively, indicating that bosutinib is at least as safe as imatinib regarding hematologic toxicity.

Ph+ Leukemia

Pooled safety data are reflected below (with a cutoff date of 15 November 2010). A total of 870 Ph+ leukemia patients across multiple, global Pfizer-sponsored clinical trials received at least 1 dose of single-agent bosutinib. These patients were either newly diagnosed Ph+ chronic phase CML, or were patients with resistant or intolerant Ph+ chronic, accelerated, or blast phase CML or Ph+ acute lymphoblastic leukemia (ALL). Of these patients, 248 are from the Phase 3 study in previously untreated CML patients, 570 and 52 are from two Phase 1/2 studies in previously treated Ph+ leukemias. The median duration of therapy was 16.6 months (range: 0.03 to 30.4 months) in the Phase 3 study, 11 months (range: 0.03 to 55.1 months), and 5.5 months (range: 0.3 to 30.4 months), in the Phase 1/2 studies respectively.

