8.2.2.8. Adverse Events of Special Interest

The number and percentage of maximum treatment-emergent CTCAE grade events and successful rechallenge for ALT, AST, thrombocytopenia (including MedDRA PT Platelet Count Decreased), neutropenia (including PT Neutrophil Count Decreased), anemia (including PT Hemoglobin Decreased), diarrhea, nausea, and vomiting will be summarized. Descriptive statistics for time to first event, duration of any grade event, and cumulative duration of grade 3/4 events will be calculated for each of these parameters.

The number and percentage of maximum treatment-emergent CTCAE grade events over time for diarrhea will be summarized. Only patients receiving treatment within a given time period will be included in the denominator for this time period. The incidence relative to the first dose of both the parent studies and the first dose of B1871040 will be calculated separately. Furthermore, the incidence relative to the last dose of bosutinib from the parent studies will also be calculated in order to see the percentage of patients experiencing diarrhea during the last 6 months prior to enrolling in B1871040. Time to first event in B1871040, defined as any new event in B1871040 or any increase in severity for ongoing events from B1871006 or B1871008, and duration of B1871040 events will also be summarized.

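### Successful rechallenge is defined without recurrence, time on drug after restart or a stated denominator, so the percentage does not show whether patients tolerated re-exposure

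*SAP*

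**What the plan says.** SAP 6.2.7 lists the characteristics to be summarised for each AE of special interest. One of them is "successful rechallenge (those patients who were re-dosed and did not discontinue bosutinib due to this AE after having a dose delay". SAP 8.2.2.8 turns this into an output: "The number and percentage of maximum treatment-emergent CTCAE grade events and successful rechallenge for ALT, AST, thrombocytopenia" and the remaining listed AEs. Neither section says what the percentage is a percentage of, whether the delay must have been for the same AE, or how long a patient must be followed after restart.

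Protocol 1.2.2 gives a parent-study result of the same type. Among bosutinib patients in B1871008 with Grade 3-4 transaminase elevations, "91% were rechallenged". The next sentence reads: "Of these patients, 80% did not experience subsequent elevations in transaminase levels that merited treatment discontinuation".

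Protocol 5.2.2 (Table 4) provides for additional episodes of Grade 3 hematologic toxicity to be handled by interruption and reduction. Recurrence while staying on bosutinib is therefore a path the protocol foresees.

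**The concern.** The rule has two inputs: the patient was re-dosed after a delay, and bosutinib was not stopped because of this AE. These patients therefore count as successes:

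- one whose AE comes back and is managed by further holds or reductions;
- one who restarts and soon afterwards stops for progression or a different AE;
- one who restarts shortly before the data end.

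A reader who sees a percentage labelled successful rechallenge is likely to take it as tolerance on re-exposure, which it does not measure. Safety is reported by cohort as well as pooled (SAP 8.2.2), and a cohort with shorter exposure has less time in which to fail; the documents do not allow this to be quantified. Diarrhea matters most, because it is the subject of the EMA commitment and SAP 6.2.7 says its characteristics will be compared between the clinical and commercial formulations.

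**Working it through.** **Inputs (all Protocol 1.2.2).**

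- B1871006 discontinuations by AE: "The most frequent AEs that led to discontinuation were thrombocytopenia (26 patients, 4.6%), ALT increased (11 patients, 1.9%), neutropenia (8 patients, 1.4"%), and 7 patients each for diarrhea and vomiting.
- B1871006 severe events: "Treatment-related TEAEs of Grade 3 or higher included thrombocytopenia in 117 (21%) patients, neutropenia in 58 (10%) patients", then diarrhea in 44 and ALT increased in 36.
- B1871006 drug-related events of any grade: thrombocytopenia 167, ALT 91, neutropenia 81, diarrhea 454.
- B1871008 bosutinib arm: 91% rechallenged and 80% of those without a later elevation meriting discontinuation; discontinuation 37% in total, 24% for AEs.

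The plan states no expected rechallenge rate. The number delayed and re-dosed is not given for any AE.

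**Step 1. Check the quoted percentages** against the 570 B1871006 patients in the pooled safety data: 26/570 = 4.6%, 11/570 = 1.9%, 8/570 = 1.4%, 7/570 = 1.2%. They agree.

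**Step 2. What an 80% success rate says about recurrence.** Let r be the proportion whose AE recurs after re-dosing, and d the proportion of those who then stop for it. If stops for this AE follow only a recurrence:

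- success under the rule = 1 − r × d;
- recurrence-free rate = 1 − r.

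With success = 0.80, r × d = 0.20. At one end r = 0.20 and d = 1.0, so 80% are recurrence-free. In between, r = 0.5 and d = 0.4 gives 50%. At the other end r = 1.0 and d = 0.20 gives 0%. The same 80% fits all three.

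**Step 3. How low the rate could be in B1871006.** Failures cannot exceed the discontinuations for that AE, so success ≥ 1 − (discontinuations ÷ number re-dosed), even if every patient recurred. The number re-dosed is an assumption, shown at three values:

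| AE | Stops | Re-dosed = Grade ≥3 related | Re-dosed = any-grade related | Re-dosed = half of Grade ≥3 |
|---|---|---|---|---|
| Thrombocytopenia | 26 | 1 − 26/117 = 77.8% | 1 − 26/167 = 84.4% | 1 − 26/58.5 = 55.6% |
| ALT increased | 11 | 1 − 11/36 = 69.4% | 1 − 11/91 = 87.9% | 1 − 11/18 = 38.9% |
| Neutropenia | 8 | 1 − 8/58 = 86.2% | 1 − 8/81 = 90.1% | 1 − 8/29 = 72.4% |
| Diarrhea | 7 | 1 − 7/44 = 84.1% | 1 − 7/454 = 98.5% | 1 − 7/22 = 68.2% |

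**Step 4. Effect of the denominator.** In B1871008, 80% of those rechallenged becomes 0.91 × 0.80 = 73% of all patients with the Grade 3-4 elevation. The SAP does not say which of these it intends.

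**Step 5. Stops for other reasons.** In B1871008, 37 − 24 = 13 of the 37 percentage points of discontinuation (35%) were not for AEs. A re-dosed patient leaving that way is a success. The share among re-dosed patients is not given.

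**Step 6. Do other outputs fill the gap?**

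- SAP 8.2.2.2 counts patients with more than one dose-change event, but not by AE.
- SAP 8.2.2.7 tabulates AEs leading to delay, reduction or discontinuation, but does not follow the re-dosed patients.
- SAP 8.2.2.8 gives cumulative Grade 3/4 duration, but not restricted to time after restart, and diarrhea over time among all treated patients.

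None shows what happened to rechallenged patients after restart.

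**The case against.** The definition stands in the SAP and openly describes staying on drug, which is a legitimate thing to measure where the protocol expects repeat episodes to be handled by interruption. The study has no hypotheses or decision rules (SAP 4.1, 4.2). This is one descriptive item, and grade, duration, dose changes and reasons for discontinuation are reported elsewhere. All of that stands and limits the weight of the point. It does not supply the missing recurrence data or the denominator.

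A reader might infer more than the documents support:

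- **That the rate is high whatever happens after re-dosing.** It is not: a stop for this AE is a failure, and the B1871008 figure implies 20% failures. The minimums in Step 3 depend on an assumed number re-dosed. They also set drug-related Grade 3 or higher events against discontinuations not described as drug-related. Nor do they carry over to B1871008. Protocol 1.2.2 says 14% there stopped for transaminase elevations, without a clear base. If that means all bosutinib patients, the same method with the 23% who had Grade 3-4 ALT elevation gives 1 − 14/23 = 39%.
- **That every death counts as a success.** A death from the same AE does so only if the reason for stopping is coded as death rather than as the AE. The SAP does not say which applies.
- **That the sponsor presents the rate as evidence that the toxicities can be managed.** Neither document says so.

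**Conclusion.** The point holds as a matter of definition and labelling. The measure records who did not stop because of this AE after re-dosing. It is uninformative about recurrence: a reported 80% leaves the recurrence-free rate anywhere between 0% and 80%, assuming that stops for the AE follow a recurrence. In B1871006 the rate could be no lower than 78% for thrombocytopenia, 69% for ALT, 86% for neutropenia and 84% for diarrhea, even with universal recurrence. That holds only if the number re-dosed equals the drug-related Grade 3 or higher cases; at half that number the minimums run from 39% to 72%. The missing denominator adds further ambiguity (80% against 73% in the one worked example). The consequence is a potentially misleading descriptive safety figure, not an error in any inferential result. It should be corrected because the remedy is cheap and no other planned table gives the information.

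**What to change.** In SAP 6.2.7 and 8.2.2.8:

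1. State the denominator as patients re-dosed after a delay for that AE, each counted once per AE from the first restart.
2. Relabel the current measure *did not discontinue due to this AE after re-dosing*, and keep it for continuity with the parent studies.
3. For the same patients, by AE and cohort, add mutually exclusive outcomes:
   - no recurrence and still on bosutinib at last follow-up;
   - recurred but continued (any grade, with Grade 3/4 shown);
   - stopped for this AE, including death from it;
   - stopped for another reason or died of another cause, with the number who had recurred first.
4. Report time on bosutinib from restart beside the table.

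The inputs are already planned: dosing records with reasons for modification (SAP 6.2.1), date and cause of death (6.2.5), and AEs with grade and resulting delays (6.2.6). No patient procedure changes. A success rule with a fixed window and grade threshold is not needed; the documents offer no basis for choosing either.

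The costs are extra programming and a less favourable headline figure. Laboratory recurrence may also be under-detected, because scheduled visits in the extension are every 6 months (B1871006 patients) or every 12 months (B1871008 patients). A footnote to the table should say so.
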